3 ELIGIBILITY CRITERIA

3.1 Inclusion Criteria

- Patients must be at least 18 years of age with evidence of progression, relapse or refractory disease from last line of therapy as defined by IMWG criteria. A line of therapy is defined as one or more cycles of a planned treatment program which may be one therapy or a sequence of treatments. A new line of therapy begins when a planned course of therapy is modified due to disease progression, relapse or toxicity or when a planned period of observation off therapy.
Measurable disease as defined by any of the following:
 - Serum M-protein ≥ 0.5 g/dl (≥ 10 g/l)
 - Urine monoclonal protein ≥ 200 mg/24h
 - Involved FLC level ≥ 10 mg/dl (≥ 100 mg/l) and an abnormal serum free light chain ratio (<0.26 , or >1.65)
 - Measurable biopsy proven plasmacytoma (should be measured within 28 days of initial investigational agent dosing)
- Patients must have exhausted all available therapies known to provide clinical benefit and has progressed, relapsed or is refractory to last line of treatment.
- Patients must have had at least 4 prior lines of therapy.
- Patient may be enrolled at any time from last line of therapy.
- Patients must have ANC $> 1000/\mu\text{L}$; Platelets $\geq 75,000/\mu\text{L}$, if plasma cell percentage on bone marrow biopsy aspirate or core is $> 30\%$, platelet eligibility requirement will be adjusted to $60,000/\mu\text{L}$.
- Patients must have adequate hepatic function as evidenced by: total bilirubin ≤ 1.5 mg/dL, alkaline phosphatase $\leq 3X$ the ULN, AST/ALT $\leq 2X$ the ULN
- Patients must have adequate renal function as evidenced by serum creatinine ≤ 2 mg/dL or calculated creatinine clearance of ≥ 40 ml/min within 14 days of registration using MDRD formula.
- Patient must be able to swallow capsule or tablet.
- Patients must provide informed consent.
- Patients must have a left ventricular ejection fraction $\geq 30\%$, no uncontrolled arrhythmias or New York Heart Association class III-IV heart failure.
- Patients must have a Karnofsky performance status ≥ 70 .
- A negative pregnancy test will be required for all women of child bearing potential. Breast feeding is not permitted.
- Fertility requirements
 - Female patients with child bearing potential must have a negative pregnancy test at least 7 days before starting treatment drugs.
 - Male patients must agree to use an adequate method of contraception for the duration of the study and for 7 months afterwards.

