6.9.6 Study Calendar Schedule of Events

Investigations	Screening	C1D1 ^a	C1D15 ^a	C2D1 ^a	C2D15 ^a	CxD1 ^a	CxD15 ^a	C12D1 ^a	Off study ^b
History, physical examination, concomitant medication review	X	X		X		X		X	X
Informed written consent	X								
Confirmation of disease relapse and prior treatment	X								
Skeletal survey (CT or MRI as clinically indicated) ^c	X								X
MUGA or ECHO	X								
β-hCG ^d	X								
Toxicity evaluation	X	X		X		X	X		X
CBC / differential / platelets ^e	X	X	X	X	X	X	X ^f		X ^f
PTT, INR, TSH ^e	X								
BMP, glucose, magnesium ^e	X	X		X		X	X		
LFTs	X	X		X		X	X		
Beta 2 microglobulin ^g	X								X
12-lead ECG ^h	X								
Serum monoclonal protein assessments ⁱ	X	X ⁱ		X ⁱ		X ⁱ			X ⁱ
24hr urine for creatinine clearance	X								
24hr urine monoclonal protein and immunofixation ^j	X	X ^j		X ^j		X ^j	X		X ^j
BM biopsy, unilateral ^k	X						X ^k		X ^k
nivolumab Given		X	X	X	X	X	X	X	

Prescribe lenalidomide via RevAssist ^l	X								
Dexamethasone ^m	X								
Pregnancy test ⁿ	X								
Correlative studies, peripheral blood ^o		X ^o	X	X	X	X	X	X	X
Correlative studies, bone marrow aspirate ^q	X					X ^q			X
Monitoring ^p	X								

- a. Time points in the preceding table have a +/- 4 day window to accommodate weekends, holidays, and for patient convenience.
- b. Off study correlates will be done. In addition, continued T-cell correlate will be done at 1,3, and 6 months after removal from study
- c. Skeletal survey will be done at baseline and may be done at evidence of progression of disease. CT scan will be done to document size of plasmacytoma if this is the only measurable disease.
- d. Female patients of childbearing potential (FCBP, defined in section 8.5) must have a negative pregnancy test (β -hCG) as required by the RevAssist program.
- e. CBC d/p will be monitored biweekly in cycles 1 to 4, then monthly thereafter. Chemistry tests, including electrolytes, glucose and serum creatinine, should be performed every 2 weeks during the first 2 months of therapy and once a month thereafter. Serum electrolyte monitoring should include potassium, magnesium and calcium. PTT, INR and TSH will be checked every 2 months.
- f. Starting C5D1, CBC will be done monthly on D1 of each cycle.
- g. Beta 2 microglobulin will be done after every 2 cycles and at evidence of progression of disease.

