- h. Baseline and periodic ECGs should be performed during treatment as indicated in the flow chart. In patients who have ECG abnormalities, ECGs should be performed more routinely as clinically indicated. ECGs post-baseline should be performed as indicated
- i. Myeloma monoclonal protein assessments (Serum protein electrophoresis & immunofixation, immunoglobulin levels, serum free light chain assay) will be performed on day 1 of each cycle as well as off study.
- j. 24hr urine monoclonal protein assessment (Urine protein electrophoresis & immunofixation) will be performed at screening and as required for response assessment.
- k. Unilateral bone marrow (BM) biopsy will be done at baseline and at end of 4th cycle and evidence of progression for patients with non-secretory multiple myeloma
- l. Lenalidomide must be prescribed through and in compliance with Celgene's RevAssist® program. Prescriptions must be filled within 7 days. Any unused lenalidomide should be returned to the patient for disposition in accordance with the RevAssist® program.
- m. Dexamethasone will be started on cycle 3 only if stable disease after 2 cycles.
- n. Lenalidomide and dexamethasone will start on day 1 of each cycle. Patients will do not need to be in clinic to initiate this as all patients would have been exposed to both. Lenalidomide will be ordered for the next cycle. A pregnancy test (urine or B-HCG) will also be ordered at this time and must be negative prior to starting treatment.
- o. Laboratory correlative studies will be obtained. This will be collected through C5D1, at the off study visit, and at 1, 3, and 6 months post off-study. Off-study correlates should be obtained at the time the patient is removed from protocol for any reason.
- p. Vital signs (temperature, blood pressure, pulse rate, respiratory rate) and ECG will be closely monitored prior to, during, and after first drug infusion to avoid general infusion-related reactions. Routine vital signs with subsequent infusions, unless indicated otherwise.
- q. Correlative studies for the bone marrow aspirate will be done at screening, cycle 5 day 1, and at the off study visit.

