		70	Cares for self, unable to carry on normal activity or to do active work.
2	In bed <50% of the time. Ambulatory and capable of all self-care, but unable to carry out any work activities. Up and about more than 50% of waking hours.	60	Requires occasional assistance, but is able to care for most of his/her needs.
		50	Requires considerable assistance and frequent medical care.
3	In bed >50% of the time. Capable of only limited self-care, confined to bed or chair more than 50% of waking hours.	40	Disabled, requires special care and assistance.
		30	Severely disabled, hospitalization indicated. Death not imminent.
4	100% bedridden. Completely disabled. Cannot carry on any self-care. Totally confined to bed or chair.	20	Very sick, hospitalization indicated. Death not imminent.
		10	Moribund, fatal processes progressing rapidly.
5	Dead.	0	Dead.

13 Appendix. IMWG Response Criteria

Serum and urine M-protein estimates will be performed every 4 weeks; except for assessment of CR, patients with measurable disease restricted to the SPEP (or UPEP) will need to be followed only by SPEP (or UPEP). Responses will be assessed according to the criteria of the International Myeloma Working Group⁴⁶, and characterized as follows:

Response Category	Response Criteria ^a
SCR	CR as defined below plus 
 • Normal FLC ration and • Absence of clonal cells in bone marrow^b by immunohistochemistry or immunofluorescence^c
CR	Negative immunofixation on the serum and urine and disappearance of any soft tissue plasmacytomas and $\leq 5\%$ plasma cells in bone marrow ^b
VGPR	Serum and urine M-protein detectable by immunofixation but not on electrophoresis or 90% or greater reduction in serum M-protein plus urine M-protein level < 100 mg per 24 hours

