PR	$\geq 50\%$ reduction of serum M-Protein and reduction in 24 hour urinary M-protein by $\geq 90\%$ or to < 200 mg per 24 hours If the serum and urine M-protein are unmeasurable ^d a $\geq 50\%$ decrease in the difference between involved and uninvolved FLC levels is required in place of the M-protein criteria If serum and urine M-protein are unmeasurable, and the serum free light assay is also unmeasurable, $\geq 50\%$ reduction in plasma cells is required in place of M-protein provided baseline bone marrow plasma cell percentage was $\geq 30\%$ In addition to the above, if present at baseline a $\geq 50\%$ reduction in the size of soft tissue plasmacytomas is also required
SD^e	Not meeting criteria for CR, VGPR, PR, or progressive disease
Relapse Category^f	Relapse Criteria
Progressive disease	Requires only one of the following: Increase of $\geq 25\%$ from baseline in: 
 • Serum M-component and/or (the absolute increase must be ≥ 0.5 g/dl)^g • Urine M-component and/or (the absolute increase must be ≥ 200 mg/24 hours) • In patients without measurable serum and urine M-protein levels the difference between involved and

	
uninvolved FLC levels, the absolute increase must be $> 10 \text{ mg/dl}$.
 
 • Bone marrow plasma cell percentage, the absolute % must be $\ge 10\%$^h. • Definite development of new bone lesions or soft tissue plasmacytomas increase in the size of existing bone lesions or soft tissue plasmacytomas. • Development of hypercalcemia (corrected serum calcium $> 11.5 \text{ mg/dl}$ or 2.65 mmol/l) that can be attributed solely to the plasma cell proliferative disorder.
Clinical relapse (Not used for TTP or PFS)	Clinical relapse requires one or more of: 
 • Development of new soft tissue plasmacytoma or bone lesions • Definite increase in the size of existing plasmacytomas or bone lesions. A definite increase is defined as a 50% (and at least 1 cm) increase as measured serially by the sum of the products of the cross-diameters of the measurable lesion • Hypercalcemia ($> 11.5 \text{ mg/dl}$ [2.65 mmol/l]) • Decrease in hemoglobin of $\ge 2 \text{ g/dl}$ (1.25 mmol/l) • Rise in serum creatinine by 2 mg/dl or more ($177 \mu\text{mol/l}$ or more)

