Relapse from CR ⁱ	Any one or more of the following: 
 • Reappearance of serum or urine M-protein by immunofixation or electrophoresis • Development of $\ge 5\%$ plasma cells in the bone marrow^j • Appearance of any other sign or progression

a. All response categories require two consecutive assessments made at anytime before the institution of any new therapy; all categories also require no known evidence of progressive or new bone lesions if radiographic studies were performed. Radiographic studies are not required to satisfy these response criteria.

b. Confirmation with repeat biopsy not necessary.

c. Presence/absence of clonal cells is based upon the κ/λ ratio by immunohistochemistry and/or immunofluorescence requires a minimum of 100 plasma cells for analysis. An abnormal ration reflecting presence of an abnormal clone is κ/λ of $> 4:1$ or $< 1:2$.

d. Applicable only to patients who have 'measurable' disease defined by at least one of the following three measurements: Serum M-protein $\ge 1 \text{ g/dl}$, Urine M-protein $\ge 200 \text{ mg/24hour}$, Serum FLC assay involved FLC level $\ge 10 \text{ mg/dl}$ provided serum FLC ration is abnormal.

e. Not recommended for use as an indicator of response; stability of disease is best described by providing the time to progression estimates).

f. All relapse categories require two consecutive assessments made at anytime before classification as relapse or disease progression and/or the institution of any new therapy.

g. For progressive disease, serum M-component increases of $\ge 1 \text{ gm/dl}$ are sufficient to define relapse if starting M-component is $\ge 5 \text{ g/dl}$.

h. Relapse from CR has the 5% cutoff versus 10% for other categories or relapse.

i. To only be used if the end point studied is disease free survival. For purposes of calculating time to progression and progression-free survival, CR patients should also be evaluated using criteria listed above for progressive disease.

j. Relapse from CR has the 5% cutoff versus 10% for other categories of relapse.

14 Appendix. NYHA Cardiac Disease

Class	Functional Capacity	Objective Assessment
I	Patients with cardiac disease but without resulting limitations of physical activity. Ordinary physical activity does not cause undue fatigue, palpitation, dyspnea, or anginal pain.	No objective evidence of cardiovascular disease.

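### A plasmacytoma-only patient with under 30% baseline marrow plasma cells is eligible but has no route to PR, however much the lesion shrinks

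*Combined protocol and SAP*

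**What the plan says.** **Eligibility.** Section 3.1 and the synopsis list four measurable-disease criteria, any one of which suffices. The fourth is "Measurable biopsy proven plasmacytoma (should be measured within 28 days of initial investigational agent dosing".

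**Calendar.** Footnote c in 6.9.6 foresees patients who enter on that criterion alone: "CT scan will be done to document size of plasmacytoma if this is the only measurable disease". The skeletal survey/CT row is marked only at screening and off study.

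**PR row, Appendix 13.** There are three marker routes:
- a fall in serum and urine M-protein;
- if those are unmeasurable, a fall of at least 50% in the FLC difference;
- if FLC is also unmeasurable, a fall of at least 50% in marrow plasma cells, "provided baseline bone marrow plasma cell percentage was" at least 30%.

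The plasmacytoma condition follows and opens with "In addition to the above, if present at baseline".

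**Footnote d, Appendix 13.** The FLC substitution is "Applicable only to patients who have 'measurable' disease defined by at least one of the following three measurements": serum M-protein, urine M-protein and FLC. Plasmacytoma is not among them.

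**CR row.** It asks for "disappearance of any soft tissue plasmacytomas", together with negative serum and urine immunofixation and no more than 5% marrow plasma cells.

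**Analysis.** Section 7.1.1 counts partial and complete responses over all eligible patients who receive any treatment. With 18 patients, 7 or fewer responses means ineffective, 10 or more effective, and 8 or 9 inconclusive.

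**The concern.** The plan admits some patients on a measure that its primary-endpoint rule cannot credit, short of complete response. For them the lesion is the only disease being tracked, yet a large reduction in it falls to the stable-disease row, which takes everyone who meets no other category. A true lesion response would be counted as a non-response.

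Two things depend on that label. The primary decision rests on a count in 18 patients with cut-offs at 7 and 10, so one or two misclassified patients matter. Sections 6 and 6.5 also allow dexamethasone to be added when there is only stable disease after 2 cycles, judged by Appendix 13. A misclassified patient may meet that condition and then enter the planned summary of conversions to response after dexamethasone.

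**Working it through.** **Step 1. Which routes are closed?** Take a patient who meets 3.1 only through the plasmacytoma.
- Serum: the 3.1 threshold is printed as 0.5 g/dl with 10 g/l (1 g/dl) in brackets. A patient below either figure is below the 1 g/dl of footnote d.
- Urine: both places use 200 mg/24h.
- FLC: both places use 10 mg/dl with an abnormal ratio.

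So a plasmacytoma-only patient under 3.1 is also unmeasurable under footnote d. The M-protein and FLC routes to PR are closed.

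**Step 2. What remains?**

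| Category | Open to this patient? | Does lesion shrinkage count? |
|---|---|---|
| PR, baseline marrow at least 30% | Yes: at least 50% marrow fall plus at least 50% lesion reduction | Only as an added condition |
| PR, baseline marrow below 30% | No | No |
| VGPR | Written only in M-protein terms | No |
| CR | Yes | Only complete disappearance, with negative immunofixation and no more than 5% marrow plasma cells |
| SD | Default | – |

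The gap is the second row.

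**Step 3. The design without the problem.** Inputs from 7.1.1: n = 18, inactivity rate 26%, activity rate 60%, cut-offs 7 and 10. With X binomial(18, p):
- P(X ≥ 10 | 0.60) = 73.7%
- P(X ≤ 7 | 0.60) = 5.8%, against a stated type 2 error of 5%
- P(X ≥ 10 | 0.26) = 0.7%, against a stated type 1 error of 5%
- P(X ≤ 7 | 0.26) = 93.0%, against a stated 80%

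The stated error rates are not reproduced exactly. That is a separate matter and does not affect this point.

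**Step 4. Size of the effect.** Let k be the number of the 18 who cannot be scored as responders, the others responding at 60%. Then X is binomial(18 − k, 0.60), and

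P(X ≥ 10) = Σ from x = 10 to 18 − k of C(18 − k, x) · 0.6^x · 0.4^(18 − k − x).

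The expected response rate is 0.60 × (18 − k)/18. The documents do not give k; 0 to 2 is an assumption.

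| k | P(X ≥ 10), effective | P(8 or 9), inconclusive | P(X ≤ 7), ineffective | Expected rate |
|---|---|---|---|---|
| 0 | 73.7% | 20.6% | 5.8% | 60.0% |
| 1 | 64.1% | 26.8% | 9.2% | 0.60 × 17/18 = 56.7% |
| 2 | 52.7% | 33.1% | 14.2% | 0.60 × 16/18 = 53.3% |

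The rows for k = 1 and 2 give these patients no chance of any response. CR stays open to them, so the true loss is at most what the table shows.

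**The case against.** A reader might infer that no plasmacytoma-only patient can ever be scored PR. The documents do not support that. Marrow percentage is not one of the four measurable-disease criteria, so such a patient may have 30% or more plasma cells; 3.1 expects some patients above 30%, because it adjusts the platelet limit for them. Footnote k of the calendar plans a marrow "at end of 4th cycle and evidence of progression for patients with non-secretory multiple myeloma". For these patients the marrow route works, and this objection stands.

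A reader might also infer that disappearance of the lesion is the only thing that can count. That fails in two ways. Disappearance alone does not make a CR. And the VGPR row has no plasmacytoma condition: read literally, a patient whose M-protein shows on immunofixation but not on electrophoresis could meet it with no change in the lesion. That is a further gap in the table, not a way of crediting shrinkage.

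Section 7.3 defines a response rate that includes stable disease, which would count the affected patient as a responder. This is no safeguard. It contradicts 7.1.1, and footnote e of Appendix 13 advises against stable disease as an indicator of response. It is a separate defect.

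Finally, the number of affected patients is unknown and may be zero, in which case nothing is lost. Dexamethasone may be added but is not mandated, so misclassification permits the addition without forcing it. Both points limit the size of the problem; neither removes the mismatch.

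**Conclusion.** The concern holds for a defined subset: plasmacytoma as the only measurable disease and less than 30% baseline marrow plasma cells. For them Appendix 13 has no PR route, and shrinkage short of CR earns nothing while they stay in the denominator. Followed as written, the rule gives a wrong result; this is more than missing detail. The textual conclusion needs no assumption.

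The size does. With one such patient the probability of declaring an active combination effective falls by at most 9.6 percentage points (73.7 − 64.1), and with two by at most 21.0 (73.7 − 52.7). The probability of wrongly declaring it ineffective rises by at most 3.4 (9.2 − 5.8) or 8.4 (14.2 − 5.8) points. These figures assume k of 0 to 2, a 60% response rate in the others and no responses in the affected patients.

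**What to change.** Reconcile the entry criterion with the response rule in one of two ways.

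(a) Add to the PR row that, when plasmacytoma is the only measurable disease and no M-protein, FLC or marrow route applies, a reduction of at least 50% in lesion size counts as PR. Size would be the sum of the products of the cross-diameters, which the appendix already uses for clinical relapse. State in footnote c that the CT is repeated at the response assessment for these patients, and say whether the two consecutive assessments in footnote a of the appendix apply to it. Leave footnote d unchanged, because it governs when FLC substitutes for M-protein.

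(b) Remove plasmacytoma as a stand-alone measurable-disease criterion from 3.1 and the synopsis, and drop the matching sentence in footnote c.

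Option (a) costs a repeat CT for the few patients concerned, or two if confirmation by imaging is required. The PR row already implies re-measuring any baseline plasmacytoma, so the measurement is not new in kind, but the calendar does not schedule it on treatment. Option (b) needs no imaging and narrows eligibility marginally. Under either option, the 7.3 response-rate definition should be reconciled with 7.1.1 as a separate correction.

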2.4 Secondary Endpoints

- To determine time to progression (TTP) and progression free survival (PFS)
- To determine overall survival (OS)
- To assess Nivolumab correlative biologic studies to assess immunomonitoring of lymphocytes subsets including T and NK cell, and *ex-vivo* assessment of immune functional activities.

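### Biochemical progression is measured from the pre-treatment value even in responders, so TTP, PFS and response duration can run on after the whole response has been lost

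*Combined protocol and SAP*

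**What the plan says.** The progressive disease row of Appendix 13 (IMWG Response Criteria) is a list in which any one item suffices. Its biochemical part reads "Requires only one of the following: Increase of" 25% or more "from baseline in" the serum M-component, the urine M-component, the free light chain (FLC) difference (where serum and urine are not measurable) or the marrow plasma cell percentage. Each has an absolute minimum; for serum it is a 0.5 g/dl increase. Footnote g adds that serum increases of 1 g/dl or more "are sufficient to define relapse if starting M-component is" 5 g/dl or above. New or growing bone lesions or plasmacytomas, and hypercalcemia, also count. Footnote f asks for two consecutive assessments.

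Two other categories could have caught a relapsing responder, but neither applies to these endpoints:

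- Clinical relapse is marked "Not used for TTP or PFS".
- Relapse from CR is kept by footnote i for disease-free survival, which this trial does not study. The footnote continues: "For purposes of calculating time to progression and progression-free survival, CR patients should also be evaluated using criteria listed above for progressive disease".

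Section 2.4 lists TTP and PFS as secondary endpoints. Section 7.3 ends both at progression or death, and ends response duration at progressive disease or death. It censors PFS at the first day of alternative therapy for patients who leave the trial before progression.

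**The concern.** Once a marker has fallen, the level that signals returning disease lies well below the pre-treatment level. A rule tied to the pre-treatment level ignores the regrowth in between. A patient in that interval no longer meets the response criteria and has a rising marker, but is still progression-free, and the response-duration clock keeps running.

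The delay arises only in patients whose marker fell, and it lengthens with the depth of the fall. It therefore favours the regimen in the patients who make up its apparent benefit. At stake are two named secondary endpoints and one further defined outcome, response duration.

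**Working it through.** **Step 1: what baseline means.** Appendix 13 gives no separate definition for the progression row. The partial response row uses the word for the pre-treatment state ("In addition to the above, if present at baseline a" 50% shrinkage of plasmacytomas is required). Calendar footnotes c and k in section 6.9.6 use it the same way, and footnote g speaks of the starting M-component. No lowest or nadir value is named anywhere in the protocol. The natural reading is the pre-treatment value.

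**Step 2: the serum threshold.** For a reference value R in g/dl, progression is met at

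T(R) = max(1.25 × R, R + 0.5), with R + 1 sufficient when R is at least 5.

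As written, R is the baseline. The alternative sets R to the lowest on-study value.

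**Step 3: numbers.** Baselines are assumed, because the protocol gives no distribution. The 0.5 g/dl case is the lowest serum value admitted by section 3.1. The gap in doublings is log2 of the ratio of the two thresholds.

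| Baseline | Lowest value | T from baseline | T from lowest value | Gap (doublings) |
|---|---|---|---|---|
| 3.0 | 1.5 (50% fall) | max(3.75, 3.5) = 3.75 | max(1.875, 2.0) = 2.0 | log2(1.875) = 0.91 |
| 3.0 | 0.3 (90% fall) | 3.75 | max(0.375, 0.8) = 0.8 | log2(4.69) = 2.23 |
| 3.0 | 0 (CR) | 3.75 | 0.5 | log2(7.5) = 2.91 |
| 1.0 | 0.5 (50% fall) | max(1.25, 1.5) = 1.5 | max(0.625, 1.0) = 1.0 | log2(1.5) = 0.58 |
| 0.5 | 0.25 (50% fall) | max(0.625, 1.0) = 1.0 | max(0.3125, 0.75) = 0.75 | log2(1.33) = 0.42 |

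At a baseline of 3.0 g/dl the partial responder must rise 2.5-fold (3.75/1.5) and the patient with a 90% fall 12.5-fold (3.75/0.3). A complete responder can go from 0 back to 3.0 g/dl, a 0% rise from baseline, without serum progression.

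**Step 4: time, as illustration only.** The protocol gives no M-protein doubling time. With exponential regrowth and an assumed doubling time of 1 to 3 months, the 0.91-doubling gap is 0.9 to 2.7 months, the 2.23-doubling gap 2.2 to 6.7 months, and the 0.42-doubling gap 0.4 to 1.2 months. These are delays for a single patient.

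**Step 5: do the other routes close the gap?** Only in part. Under footnote c a skeletal survey after baseline is optional and follows evidence of progression. Under footnote k a repeat marrow biopsy is scheduled only for non-secretory disease. A purely biochemical relapse in secretory disease rests on the M-protein or FLC rule.

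**The case against.** The strongest reply concerns consequence. The primary endpoint is the response rate after 4 cycles (section 2.1). Neither the 18 patients nor the cut-offs of 7 or fewer, 8 or 9, and 10 or more responders (section 7.1.1) use the progression reference. Section 7.1.1 calls the PFS analysis exploratory, the trial has one arm, and response duration is defined in section 7.3 without being listed as an endpoint. All of this stands and limits the severity.

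It is also fair to say that other events may come first. A bone lesion, plasmacytoma, hypercalcemia or death ends the clock. A patient switched to new therapy before formal progression is censored for PFS, so the calculated delay is not what would be recorded. It would be too strong to say that all three measures are overstated in every responder.

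A reader might make three further inferences that the documents do not support:

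- **That the median shifts by the months in step 4.** No such shift follows. At a 26% response rate about 13 of 18 patients would not respond (18 × 0.74 = 13.3), and the median could move little.
- **That the results can no longer be compared with the TTP and PFS figures in section 1.3.1.** No such comparison is planned; the only historical cut-offs are the response rates of 26% and 60%. The protocol does not give the progression reference used in those studies.
- **That the table departs from its cited source.** That cannot be checked from the protocol.

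If the sponsor meant baseline as the lowest response value, the text does not say so, and sites could date progression differently. A clarification is needed on either reading.

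**Conclusion.** The point holds, at moderate severity. Followed as written, the rule dates biochemical progression later than a lowest-value reference would in patients whose marker fell, and TTP, PFS and response duration inherit the delay unless another event or censoring comes first. The direction and the thresholds follow from the text and arithmetic, given that baseline means the pre-treatment value. The size depends on the baseline level and the depth of response: for a partial response, 0.42 doublings at 0.5 g/dl and 0.91 at 3.0 g/dl; for a 90% fall, 2.23 at 3.0 g/dl. Any figure in months also rests on the assumed doubling time. The primary analysis and the decision rule are unaffected.

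**What to change.** For the analysis of TTP, PFS and duration of response:

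- In the marker criteria of the Appendix 13 progressive disease row (serum, urine, FLC difference, marrow), make the reference the lowest value recorded from Cycle 1 Day 1 onward, inclusive, in place of baseline.
- Keep the listed absolute minimums and the two consecutive assessments of footnote f. These also limit the influence of one stray low reading.
- Tie the 5 g/dl condition in footnote g to the same reference, and state in footnote i that complete responders are judged by it.

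Sections 5.2, 5.3 and 6.8 end study therapy at progression, and Appendix 13 holds the only definition of progression. The sponsor must reconcile those passages with the endpoint definition. No treatment-stopping rule is proposed here.

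The cost is an amendment to one table row and two footnotes, plus that reconciliation. No new serum sampling is needed, since section 6.9.6 (footnote i) already has serum markers on day 1 of each cycle. The downside is that reported TTP, PFS and response duration become somewhat shorter.
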